2.2 Collected Data

The following data will be collected for both the exam acquired by the expert and the exam acquired by the novice:

- Whether the exam was acquired by the expert/novice,
- Reason for not acquiring the exam,
- Whether the exam has successfully been exported for review by the cardiologists,
- Number of clips acquired by the expert/novice,
- Novice acquisition duration in minutes,
- Report of Adverse event (AE) with details, start and end date, severity, relationship, action taken and outcome,
- Report of Device deficiency (DD) with details, date, type, and reason of deficiency, action taken and outcome,
- Report of Serious adverse event (SAE) with details, start and end date, severity, relationship, action taken, and outcome.

The following data will be collected for each review performed by each cardiologist on each exam for qualitative assessment:

- Qualitative assessments
- For the 10 reference views of cardiac ultrasound (PLAX, PSAX-PM, PSAX-MV, PSAX-AV, A4C, A5C, A2C, A3C, SC-4C and SC-IVC), quality of diagnostic (Yes/No/No clip),
- Qualitative visual assessment of left ventricular size (Yes/No) and type* (if Yes),
- Qualitative visual assessment of left ventricular function (Yes/No) and type* (if Yes),
- Qualitative visual assessment of right ventricular size (Yes/No) and type* (if Yes),
- Qualitative visual assessment of right ventricular function (Yes/No) and type* (if Yes),
- Qualitative visual assessment of non-trivial pericardial effusion (Yes/No) and type* (if Yes),
- Qualitative visual assessment of left atrial size (Yes/No) and type* (if Yes),
- Qualitative visual assessment of right atrial size (Yes/No) and type* (if Yes),
- Qualitative visual assessment of segmental kinetics of the left ventricle (Yes/No) and type* (if Yes),
- Qualitative visual assessment of aortic valve (Yes/No) and type* (if Yes),
- Qualitative visual assessment of mitral valve (Yes/No) and type* (if Yes),
- Qualitative visual assessment of tricuspid valve (Yes/No) and type* (if Yes),
- Qualitative visual assessment of inferior vena cava size (Yes/No) and type* (if Yes).

* For each assessment, the type will be described in section 3.4.1.

The following data will be collected for each review performed by each cardiologist on each exam for quantitative assessment:

- For PLAX clip:
 - If measurement = Yes, IVSd, LVEDD, and PWd measurement (in mm),
 - If measurement = Yes, LVESD measurement (in mm),
 - If measurement = Yes, Aortic root measurement (in mm),
- For A4C clip:
 - If measurement = Yes, A4C single-plane LV EDV and LV ESV measurement (in mL) and LV EF measurement (in %),
- For A2C clip:
 - If measurement = Yes, A2C single-plane LV EDV and LV ESV measurement (in mL), LV EF measurement (in %),
- For A4C and A2C clips:
 - If measurement = Yes, Biplane LV EDV and LV ESV measurement (in mL) and Biplane LV EF measurement (in %),
- For SC-IVC clip:
 - If measurement = Yes, Diameter of the IVC measurement (in mm).

The following data will be collected for each patient:

- Information regarding consent form and eligibility criteria,
- Information regarding premature discontinuation (date of end of study and reason for study exit),
- Demographics (age, sex, height, weight, BMI, ethnicity*, race*),
- Indication for cardiac ultrasound exam,
- Prior cardiac diagnoses (hypertension, hyperlipidemia, diabetes, heart failure, atrial fibrillation, other arrhythmias, coronary artery disease, prior heart attack, valvular heart disease, pulmonary hypertension, heart transplant, cardiomyopathies, congenital heart disease, other and specification of other prior cardiac diagnoses, none, not reported),
- Prior non-cardiac diagnoses (renal disease, COPD/emphysema, pulmonary embolus, systemic infiltrative disease like amyloid or hemochromatosis, cancer, underwent chemotherapy, underwent radiation, other and specification of other prior non-cardiac diagnoses, none, not reported),
- Implanted medical devices (pacemaker/ICD, leadless pacemaker, prosthetic heart valve, LAA closure device, atrial septal defect closure device, ventricular septal defect closure device, patent foramen ovale closure device, valve repair device, other and specification of other implanted medical devices, none, not reported),
- Cardiac abnormalities (abnormal left ventricular size or function, abnormal right ventricular size or function, abnormal left atrial size, abnormal right atrial size, septal defect, abnormal mitral valve, abnormal tricuspid valve, abnormal aortic valve, non-trivial pericardial effusion, abnormal inferior vena cava size, patent foramen ovale, other and specification of other cardiac abnormalities, none, not reported).

* Only collected for US patients.

2.3 Eligibility Criteria

2.3.1 Inclusion Criteria

The inclusion criteria are:

- patient (male or female) over 18 years old,
- patient having an echocardiography exam scheduled in an investigated center,
- patient who has given his consent to participate in the research and signed consent form,
- patient affiliated with social security (for France only).

2.3.2 Exclusion Criteria

The exclusion criteria are:

- patient subject to a measure of legal protection (safeguard of justice, guardianship, or curatorship),
- patient deprived of liberty by judicial or administrative decision,
- patient unable to give his consent,
- pregnant or breastfeeding women (declarative),
- patient with cardiac anatomy that does not allow reference electrocardiographic sections to be made (situs inversus, single ventricle, congenital anomalies, etc.),
- patient having benefited from prior echocardiographic exams whose reports mention poor or weak echogenicity,
- patient having known chest deformity that has already been mentioned in previous reports or has been the subject of investigations (*pectum excavatum*),
- patient who has undergone total or partial pneumonectomy.

3. Study Objectives

The primary hypothesis is that novices without previous experience in ultrasound examination could obtain diagnostic-quality acquisitions with the software HeartFocus.

3.1 Primary Objective

The primary objective of the study is to evaluate if ultrasound exams, performed with the HeartFocus software by novices (nurses without prior ultrasound experience), allow the qualitative visual assessment of

- left ventricular size,
- global left ventricular function,
- right ventricular size,
- non-trivial pericardial effusion.

3.2 Secondary Objectives

The secondary objectives are:

- to evaluate the agreement between the acquisitions obtained by experts and those obtained by novices in terms of quality and echocardiographic parameters,
- to evaluate the impact of the investigating centers, prior cardiac diagnoses, and obese patients on the quality of ultrasound exams,
- to evaluate the time to acquire a limited ultrasound exam for a novice with the HeartFocus software,
- to evaluate the performance of HeartEF to automatically calculate the ejection fraction.

3.3 Primary Endpoints

The entire exam allows the qualitative visual assessment of

- left ventricular size (yes, no),
- global left ventricular function (yes, no),
- right ventricle size (yes, no),
- non-trivial pericardial effusion (yes, no).

All endpoints will be assessed by 5 different cardiologists, from the independent review committee. The criteria will be assessed on the exams obtained by novices and those obtained by experts, for each patient.

Success Criteria

The lower limit of the 95% confidence interval (CI) around the percentage of exams that have sufficient quality to allow the qualitative visual assessment of

- left ventricular size,
- global left ventricular function,
- right ventricle size,
- and non-trivial pericardial effusion

are all strictly above 80%.

3.4 Secondary Endpoints

3.4.1 Quality Endpoints

These endpoints will assess the quality of the exams. They complement the primary endpoints.

The entire exam allows the qualitative visual assessment of

- right ventricular function (yes, no),
- left atrial size (yes, no),
- right atrial size (yes, no),
- segmental kinetics of the left ventricle (yes, no),
- aortic valve (yes, no),
- mitral valve (yes, no),
- tricuspid valve (yes, no),
- inferior vena cava size (yes, no).

Diagnostic quality clip for

- apical 2-chamber (yes, no, no clip),
- apical 3-chamber (yes, no, no clip),
- apical 4-chamber (yes, no, no clip),
- apical 5-chamber (yes, no, no clip),
- parasternal long axis (yes, no, no clip),
- parasternal short axis at the aortic valve (yes, no, no clip),
- parasternal short axis at the mitral valve (yes, no, no clip),
- parasternal short axis at the papillary muscles (yes, no, no clip),
- subcostal 4-chamber (yes, no, no clip),
- subcostal inferior vena cava (yes, no, no clip).

3.4.2 Clinical Endpoints

3.4.2.1 Qualitative Endpoints

Indicate the evaluation when the entire exam allows the qualitative visual assessment of

- left ventricular size (normal or borderline, hypertrophy, dilation, hypertrophy and dilation),
- global left ventricular function (normal or borderline, reduced (EF ≤ 50 %)),
- right ventricular size (normal or borderline, hypertrophy, dilation, hypertrophy and dilation),
- non-trivial pericardial effusion (absent, present),
- right ventricular function (normal or borderline, reduced),
- left atrial size (normal or borderline, abnormal (enlarged)),
- right atrial size (normal or borderline, abnormal (enlarged)),
- segmental kinetics of the left ventricle (normal or borderline, abnormal),
- mitral valve (structurally normal, structurally abnormal, suspected device),
- tricuspid valve (structurally normal, structurally abnormal, suspected device),
- aortic valve (structurally normal, structurally abnormal, suspected device),
- inferior vena cava size (normal, dilated),

Any other abnormalities (free text) that can be visually assessed will be described in listings.

NB: For visual assessment of left ventricular size and right ventricular size, the choices "hypertrophy," "dilation," and "hypertrophy and dilation" can be grouped in a more general category: "abnormal (enlarged)."

3.4.2.2 Quantitative Endpoints

The exam allows the quantitative evaluation of

- the septal wall thickness (in mm), the posterior wall thickness (in mm), the internal end-systolic and end-diastolic diameter of the left ventricle (in mm), and the diameter of the aortic root (in mm),
- the left ventricular end-systolic and end-diastolic volumes (in mL), and the left ventricular function (ejection fraction in %) via both the Simpson Biplane method using the cardiologists' segmentations and the HeartEF algorithm developed by DESKi,
- the diameter of the inferior vena cava (in mm).

3.4.3 Duration Endpoint

Acquisition time (in minutes) required to obtain the acquisitions of the 10 reference views for the novices.

3.5 Sample Size Justification

The main hypothesis for the sample size calculation is based on the sequential testing of the four primary endpoints (the left ventricular size, the left ventricular function, the size of the right ventricle, and the presence of non-trivial pericardial effusion) with the performance goal of 80% (each lower 2-sided 95% CI limit for each parameter should be greater than 80%).

As the study design is like the pivotal trial, conducted by a US team, which led to FDA certification of our competitor software to assist novices in performing cardiac ultrasound acquisitions, we based our sample size calculation on the sample size calculation of the pivotal trial. This pivotal trial included 240 patients and 8 different operators. Each operator performed the acquisitions on 30 patients.

The elements for the sample size calculation of the pivotal study are described below:

- the pivotal study was powered to detect the primary endpoint's exceeding the performance goal of 80% ($\alpha = 0.05$, $\beta = 0.2$),
- the statistical power was estimated using iMRMC 4.0 software developed by the FDA, which provides the 95% CI around the point estimate for a given parameter and was used for the primary endpoint analysis,
- the sample size (240 patients and 8 different operators who performed the acquisitions on 30 patients) would have a statistical power of 0.98 for each parameter or greater than 0.92 for 4 sequentially tested parameters.

4. Statistical Methodology

4.1 Definitions and Conventions

Statistical analyses will be carried out by a qualified biostatistician using SAS® software (V9.4 or later), R (CRAN), or specific software for multi-reader multi-case (MRMC) study analysis.

Qualitative variables will be described using the number of filled and missing data and, for each modality, the frequency and percentage (referring to filled data). Proportions will be estimated with their exact (binomial) 95% CIs when appropriate.

Quantitative variables will be described using the number of filled and missing data, arithmetic mean, standard deviation, median, 1st and 3rd quartiles, minimum, and maximum. Means will be further described with 95% CIs when appropriate. They can also be presented in class (e.g. age groups) and described in the form of categorical variables, based on quartiles and medians or known clinical thresholds.

Statistical tests will be two-sided at a level of type I error alpha set to 5%. All confidence intervals will be two-sided and presented at the 95% confidence level.

Comparisons of two or more qualitative variables are made using the χ^2 test or Fisher exact test, according to the expected values under the assumption of independence. Comparison of quantitative variables according to 2 groups are made using a Student test or Mann-Whitney-Wilcoxon test (nonparametric test comparing ranks) depending on the distribution of the variable of interest. Transformations to normalize the distribution of the variable can be performed if necessary.

Correlations are made using the Pearson/Spearman correlation coefficient depending on the type of correlation.

4.2 Analysis Populations

4.2.1 Screened Population

All patients who signed an informed consent form.

4.2.2 Eligible Population

All patients from the screened population who met the eligibility criteria.

4.2.3 Full Analysis Set (FAS) Population

All patients from the eligible population with at least the exam performed by the novice. This population will be used for the analyses of primary and secondary endpoints.

NB: Only patients from the FAS population who have both exams will be used for the comparison of primary and secondary endpoints between novices and experts.

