4.3 Handling of Missing Data

Missing data will not be replaced in the statistical analysis. The number of missing data will be specified in the analysis.

5. Analysis Plan

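### The primary analysis set requires a performed novice exam, so novice attempts that fail outright drop out of the percentage judged against 80%

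*SAP*

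**What the plan says.** - **Population.** SAP section 4.2.3 admits to the full analysis set (FAS) "All patients from the eligible population with at least the exam performed by the novice". The word *performed* is not defined. Section 5.4.1 runs the primary analysis on this set.
- **Success criterion.** Section 3.3 requires the lower 95% confidence limit for the "percentage of exams that have sufficient quality to allow the qualitative visual assessment of" each of the four targets to lie strictly above 80%, for all four.
- **Hypothesis.** Section 3 states it as: "novices without previous experience in ultrasound examination could obtain diagnostic-quality acquisitions with the software HeartFocus".
- **Failures foreseen.** For each exam, section 2.2 records whether it was acquired, the "Reason for not acquiring the exam", and "Whether the exam has successfully been exported for review by the cardiologists". Section 5.7 allows for patients examined by the expert only.
- **Partial exams.** Each view is rated for "quality of diagnostic (Yes/No/No clip"), so an exam with missing views still goes to the readers. No equivalent category exists for a whole exam.
- **Missing data.** Section 4.1 gives, "for each modality, the frequency and percentage (referring to filled data"). Section 4.3 adds: "Missing data will not be replaced in the statistical analysis".
- **Reporting.** Section 5.1 describes FAS exclusions with reasons and counts the patients whose novice exam has all five reviews.

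**The concern.** The trial asks whether a novice using the software can obtain an assessable exam. A novice who starts and cannot produce one, or whose exam is lost to a device fault, is a direct counter-example. If entry to the analysis set depends on the exam having been performed, that counter-example is removed before the percentage is calculated. The bias runs one way: each operator or device failure left out can only raise the figure compared with 80%. Losses for patient or logistic reasons need not bias it, but the SAP treats all reasons alike.

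An exam performed but not exported raises a second question. The patient meets the FAS wording but has no readings. If section 5.4.1 is not settled in advance, the choice could be made once results are known. All four endpoints must pass, so one reversed endpoint changes the study's conclusion.

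**Working it through.** **1. What happens to each kind of loss**

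| Situation | In the FAS? | Primary endpoint value |
|---|---|---|
| Some views missing | Yes | Read by all five cardiologists; handled |
| Not acquired, any reason | No, on the plain reading of *performed* | None; outside the denominator |
| Performed, not exported | Yes | Unclear: the filled-data and no-replacement rules (4.1, 4.3) suggest it is dropped; the 3-of-5 rule (5.4.1) can be read as not achieved |

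**2. Inputs**

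- From the SAP: 240 patients as 8 novices × 30 (2.1); goal 80%, two-sided 95% interval (3.3, 3.5); power 0.98 per parameter and above 0.92 for four (3.5).
- Assumed: the number of lost exams *k*, the success rate *p* among read exams, and 240 attempts. Exact (Clopper-Pearson) limits stand in for the MRMC interval. One endpoint is considered at a time, and every assumed loss is taken as an operator, image-quality or device failure.

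**3. The plan's own figure**

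For four independent tests, 0.98⁴ = 0.922, which matches the stated value above 0.92. The SAP gives no true success rate behind the 0.98. Under the binomial stand-in, the smallest passing count is 205/240 (85.4%, lower limit 80.3%); 204/240 gives 79.8% and fails. P(X ≥ 205 of 240) = 0.979 at a true rate of 89.4%, so 89.4% serves as the reference rate.

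**4. Losses that reverse a pass**

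For each *p*, this is the smallest *k* for which x = round(p × (240 − k)) passes over 240 − k but fails over 240.

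| Success among read exams | k | k/240 | Lower limit, losses excluded | Lower limit, losses counted as *No* |
|---|---|---|---|---|
| 86% | 3 | 1.2% | 204/237: 81.0% | 204/240: 79.8% |
| 88% | 8 | 3.3% | 204/232: 83.0% | 79.8% |
| 89.4% | 12 | 5.0% | 204/228: 84.7% | 79.8% |
| 90% | 13 | 5.4% | 204/227: 85.2% | 79.8% |
| 92% | 18 | 7.5% | 204/222: 87.5% | 79.8% |
| 95% | 25 | 10.4% | 204/215: 91.0% | 79.8% |

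At the boundary, two losses are enough: 203/238 has a lower limit of 80.15%, while 203/240 has 79.4%.

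**5. Chance that one endpoint's verdict reverses**

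With k ~ Binomial(240, f) and x ~ Binomial(240 − k, p), this is the probability that x passes over 240 − k while x ≤ 204, summed over k.

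| p | f = 0.5% | 1% | 2% | 3% | 5% |
|---|---|---|---|---|---|
| 88% | 4.5% | 9.5% | 21.7% | 36.5% | 64.1% |
| 89.4% | 1.6% | 3.8% | 10.8% | 21.8% | 51.4% |
| 92% | 0.0% | 0.1% | 0.7% | 2.6% | 15.3% |
| 95% | 0.0% | 0.0% | 0.0% | 0.0% | 0.6% |

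**6. A wider interval**

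If patients of the same novice are correlated, with an assumed coefficient of 0.02 or 0.05, the design effect is 1 + 29 × 0.02 = 1.58 or 1 + 29 × 0.05 = 2.45. Dividing x and n by it and repeating step 4, at 90% success 10 or 6 losses reverse a pass instead of 13; at 95%, 22 or 18 instead of 25. A narrower interval would need more losses.

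**The case against.** *Performed* is undefined, and the SAP never equates it with *acquired*. A failed attempt might be meant to count as performed, be marked as having no clips, and fail the 3-of-5 rule. That reading is possible, but an exam recorded as not acquired does not ordinarily count as performed. If it is the intended reading, the SAP needs a sentence saying so.

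The primary objective (section 3.1) asks about exams performed by novices, so image quality given a completed exam is a documented target. This is a fair point: the hypothesis and the objective pull in different directions. It does not put failed attempts back into the result.

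The commonest image problems, poor clips and missing views, are already read and scored, so only whole-exam losses are at issue. Their frequency is unknown and may be small. The SAP has an open reason field and does not itself name operator, image-quality or device failure. These limits stand and bound the size of the problem.

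The plan also speaks of 240 exams acquired by novices, so the true comparison might be x/240 against x/(240 + k). That would change the figures but not the direction.

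Finally, section 5.1 makes losses visible, and a reader could recompute a worst case. That is true, but no rule or planned sensitivity analysis carries the losses into the pass/fail decision.

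**Conclusion.** The concern holds. On its plain reading, the FAS rule removes outright novice failures from the primary denominator, in the direction that favours success; for exams not exported the SAP is ambiguous. The consequence is conditional. It matters if operator or device losses are not negligible or if success lies near the goal. At the reference rate of 89.4%, assumed losses of 2%, 3% and 5% reverse one endpoint's verdict with probability 10.8%, 21.8% and 51.4%. At 92% success and losses up to 3% the probability is at most 2.6%, and at 95% it is practically nil. These figures rest on assumed loss rates, the binomial stand-in and 240 attempts; the direction of the bias does not. The point should be fixed before analysis.

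**What to change.** - In 4.2.3, define the primary set as all eligible patients in whom the novice exam was started, and state that denominator in 5.4.1.
- Score as *No* on all four primary endpoints any started exam that was not acquired or not exported for an operator, image-quality or device reason, using the reason and export fields in 2.2.
- Exclude from the primary percentage, and report with reasons, patients in whom no attempt was made and started exams lost for a documented patient or logistic reason.
- Add a sensitivity analysis that counts every eligible patient without novice readings as *No*. It bounds the judgement involved in attributing reasons.
- Minor: section 4.2.4 also requires an exam performed, so a device deficiency that blocked both exams falls outside the safety listings. Define the safety set by exams started.

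The cost is SAP wording only, since the fields are already collected. The success percentage may be slightly lower, and it will then reflect acquisition failure as well as image quality.

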4.2.4 Safety Analysis Set (SAF) Population

All patients from the eligible population with at least one exam performed. This population will only be used for the safety analysis.

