DESKi	PROSPECTIVE EVALUATION OF HEARTFOCUS: A SOFTWARE SUPPORTING THE ACQUISITION OF CARDIAC ULTRASOUND EXAMS	HF-01 Version:4.2
-------	---------------------------------------------------------------------------------------------------------	----------------------

Protocol title	PROSPECTIVE EVALUATION OF HEARTFOCUS: A SOFTWARE SUPPORTING THE ACQUISITION OF CARDIAC ULTRASOUND EXAMS
Version Date	23/12/2023
NCT	NCT05874128

DE SKI	PROSPECTIVE EVALUATION OF HEARTFOCUS: A SOFTWARE SUPPORTING THE ACQUISITION OF CARDIAC ULTRASOUND EXAMS	HF-01 Version:4.2
---------------	----------------------------------------------------------------------------------------------------------------	------------------------------------

PRIMARY HYPOTHESIS	
The primary hypothesis is that novices without previous experience in ultrasound examination could obtain diagnostic-quality acquisitions with the software HeartFocus.

OBJECTIVES	
The primary objective of the study is to evaluate if ultrasound exams, performed with the HeartFocus software by novices, nurses without prior ultrasound experience, are of sufficient quality to analyze visually:
 
 
• The left ventricular size,
 
• The left ventricular function,
 
• The right ventricular size,
 
• The presence of non-trivial pericardial effusion.
 
 
The secondary objectives are:
 
 
• To evaluate the agreement between the acquisitions obtained by experts and those obtained by novices in terms of quality and echocardiographic parameters (secondary endpoints 1 to 4)
 
• To evaluate the impact of the investigating centers, prior cardiac diagnoses, and obese patients on the quality of ultrasound exam
 
• To evaluate the time to acquire a limited ultrasound exam for a novice with the HeartFocus software.
 
• To evaluate the performance of HeartEF, to automatically calculate the ejection fraction
 

NUMBER OF SUBJECTS	
240 patients will be included, 120 in Site 01 and 120 in Site 2
 
As part of their training, novices will practice cardiac ultrasound acquisition on 72 patients (36 in Site 01 and 36 in Site 2). Those patients will be not included in the analysis. They will sign a different consent form.

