5.6 Safety Analyses

All safety analyses will be performed using the safety analysis set.

A listing will be provided for

- all adverse events,
- all device deficiencies,
- all serious adverse events.

A separate listing will be provided for

- events leading to study discontinuation,
- events leading to death.

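### The safety set is filtered by eligibility, so a patient who was scanned but did not meet the criteria drops out of every planned safety table and listing

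*SAP*

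**What the plan says.** The SAP builds its sets in sequence.

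- Screened (SAP 4.2.1): "All patients who signed an informed consent form".
- Eligible (SAP 4.2.2): "All patients from the screened population who met the eligibility criteria". No time point is given for that judgement.
- Safety analysis set (SAP 4.2.4): "All patients from the eligible population with at least one exam performed".
- Use (SAP 5.6): "All safety analyses will be performed using the safety analysis set". The listings of adverse events, serious adverse events and device deficiencies come under this sentence.

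SAP 2.2 collects reports of adverse events, device deficiencies and serious adverse events for novice and expert exams alike, and attaches no eligibility condition.

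The protocol synopsis (Number of Subjects) describes a further 72 patients, 36 per site, on whom the novices practise during training. It says of them: "Those patients will be not included in the analysis". It adds: "They will sign a different consent form". The SAP does not mention these patients.

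**The concern.** Restricting an efficacy set to eligible patients can be defended. A safety set serves another purpose: it should contain everyone exposed to the study procedure, because an event counts whether or not the patient should have been enrolled. Here the safety set carries the same eligibility filter as the full analysis set. If a scanned patient is later judged ineligible, any event or device deficiency in that patient is collected but has no place in the planned output. The trial is meant to support FDA and CE certification, so a reader of its safety tables will expect them to cover all scanned study patients.

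The training patients raise a smaller, separate question. They too are scanned by the novices, and the SAP is silent on how any event in them would be presented.

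**Working it through.** **1. Trace a scanned, ineligible patient through the sets.**

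| Step | Rule | Result |
|---|---|---|
| Screened (4.2.1) | consent signed | in |
| Eligible (4.2.2) | criteria met | out |
| Full analysis set (4.2.3) | eligible, with a novice exam | out |
| Safety set (4.2.4) | eligible, with any exam | out |
| Safety output (5.6) | safety set only | not shown |

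No other safety population is defined. As written, the safety set adds to the full analysis set only those eligible patients who had an expert exam and no novice exam.

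**2. Can ineligibility emerge after the scan?** Most criteria in SAP 2.3 can be known beforehand. Some might surface later: cardiac anatomy that prevents the reference views could be revealed by the scan itself, and a previous report of poor imaging could be found afterwards. SAP 5.1 already plans to count patients outside the eligible population and give the reasons.

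**3. Size of the eligibility gap.** The documents give no rate, so this is a range by assumption. The planned number is 120 + 120 = 240, which agrees with 8 novices × 30 patients = 240.

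| Assumed share ineligible after scanning | Patients left out | Safety set |
|---|---|---|
| 0% | 0 | 240 |
| 1% | 240 × 0.01 = 2.4, about 2 | 238 |
| 2% | 240 × 0.02 = 4.8, about 5 | 235 |
| 5% | 240 × 0.05 = 12 | 228 |

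**4. Scans begun but not completed.** SAP 2.2 records whether each exam was acquired and, if not, why. Suppose a device deficiency stops the acquisition and the patient has no other exam. That patient may not count as having had an exam, so the deficiency could remove itself from the listing. This is why the fix below refers to scans started.

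**5. Training patients.** 36 + 36 = 72. Planned scanned patients in total: 240 + 72 = 312. Share in training: 72 / 312 = 23.1%. Read literally, SAP 4.2.1 does not say which consent form it means and could admit these patients. The synopsis excludes them from the analysis and gives them a separate form, so the better reading is that they are outside all SAP sets.

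**The case against.** The strongest case on the other side has four parts.

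- **The number may be zero.** Most criteria can be checked before scanning, and SAP 5.1 makes exclusions and their reasons visible. This stands. It limits the weight of the point but does not repair the definition, since the events of excluded patients would still not be tabulated or listed.
- **An analysis set does not govern data capture.** A reader might infer that events in ineligible patients would go unrecorded or unreported. The documents do not support that: SAP 2.2 collects the reports regardless of eligibility, and the supplied protocol is a synopsis with no safety-reporting section. The gap is in the planned output only.
- **The exclusion of training patients is deliberate.** The synopsis states it, and its Study Duration entry treats inclusion for training and inclusion for analysis as two groups. This stands too. A listing for them would add to the plan; it would not correct a contradiction. Whether their events are captured under the full protocol or the training consent cannot be seen from these documents.
- **The procedure is light.** It is a limited ultrasound exam, about 40 additional minutes in the study and about 30 in training, and SAP 5.6 plans only counts, proportions and listings, with no safety hypothesis or threshold. This stands and keeps the point minor.

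A reader might also infer that device or use problems are most likely in the practice scans. That is plausible, but no text in either document supports it, and supervision during training is not described. Nor should the 72 be pooled with the 240 to claim a tighter bound on event rates: a separate listing leaves the safety set at about 240.

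**Conclusion.** The point holds as a flaw of definition. SAP 4.2.2, 4.2.4 and 5.6 together remove any scanned patient who did not meet the criteria from all planned safety output, and nothing else in the SAP restores them. The numerical effect is unknown and may be nil; under the assumed 1% to 5% it is 2 to 12 of 240 patients. The primary endpoints, the sample size and the efficacy sets are untouched.

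The training-patient part is secondary. The figure of 23% describes how many planned scanned patients the SAP does not address. It says nothing about the size of the eligibility gap and should not be used to add weight to it. Overall the practical weight is minor: a cheap improvement.

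**What to change.** 1. Redefine the safety analysis set in SAP 4.2.4 as all patients who consented to the main study and in whom at least one study scan, novice or expert, was started, regardless of eligibility. Leave the efficacy sets unchanged.
2. Naming the main-study consent in that definition also settles which form counts. SAP 4.2.1 should use the same wording.
3. Optional: add a separate listing, not pooled with the safety set, of any adverse events, serious adverse events and device deficiencies recorded in the 72 training patients, if the training consent allows it.

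The cost is a change of SAP wording, one extra listing and a check of the training consent.
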